7.5. Study Size

The focus of the sample size calculations is to determine the precision of the estimated HR that can potentially be achieved in the study depending on estimated patient accrual, event rates, and assumed true risk. Because of the CHMP’s concerns related to endometrial safety, endometrial hyperplasia and endometrial cancer are the primary endpoints and were used for these sample size calculations.

Precision is a measure inversely related to variance in estimation. For the HRs being estimated in this study, precision is represented by the width of two-sided 95% CI.

Duavee estimates are projections based on Pfizer commercial forecasts of product uptake only; no patient data are yet available. Projections are conservative and assume a reduction of 50% from the original US market forecasts. The estimated number of E+P HRT new users, their total person-time of follow-up, and the expected number of incident endometrial safety events observed in that cohort was obtained based on pilot analyses of the HIRD from the last three years. Therefore, the most recent 3 years of E+P HRT use in the HIRD is being used to project future E+P HRT uptake and use.

In the HIRD pilot analyses, the number of new users of E+P HRT products (i.e., patients with at least 12 months of continuous eligibility prior to the first use of E+P HRT) were identified using a one-, two-, and three-year time frame: 01 January 2011 – 31 December 2011, 01 January 2011 – 31 December 2012, and 01 January 2011 – 31 December 2013. The total person-time of follow-up accrued by the E+P HRT new users was calculated during these periods of interest together with the number of endometrial cancer and endometrial hyperplasia events occurring after the start of E+P HRT use.

All estimates (Table 1) were calculated with two-sided 95% CIs. According to the study plan, there will be a 4-year accrual period and patients will be followed for at least 1 year, with the first two cohorts being followed for a longer duration.

Table 1. Estimated 95% Confidence Intervals for Hazard Ratios of Endometrial Safety

Description	First Annual Report	Second Annual Report	Third Annual Report
Estimated numbers of new users of Duavee ^a	1,800	3,600	5,400
Estimated numbers of new users of E+P HRT ^b	36,651	44,122	50,350
Estimated person-years of follow-up for E+P HRT users ^b	27,768	58,399	89,438
Estimated endometrial cancer events after the start of E+P HRT use ^b	29	62	80
HRs (95% CI)			

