7.7.2. Sub Analyses

Women with a previous history of E+P HRT use, different from their index drug (i.e., *Duavee* or specific E+P HRT) require special analytic considerations. In a new-user cohort design (as in the main analysis), these types of patients are excluded for several reasons. First, if women with past use of HRT incur a study endpoint, it is difficult to determine whether the endpoint is due to previous HRT or current HRT use. Further, women for whom previous HRT use was associated with poor outcomes (e.g., adverse effects) are likely to be under represented among those initiating *Duavee* or E+P HRT, which would deplete susceptible women and result in a survivorship bias or could lead to channeling of these

patients to one study drug over the other. Finally, baseline factors of women with previous use of HRT (e.g., comorbidities) could include effects of HRT (e.g., uterine bleeding) that could be intermediate in the causal pathway between exposure and study endpoints (e.g., endometrial hyperplasia, endometrial cancer). Controlling for factors that are intermediate in the causal pathway under study is to be avoided as it can invalidate a given analysis. Because of these limitations, analyses of the primary and secondary endpoints among *Duavee* and E+P HRT exposed patients with a previous history of HRT use will be limited to estimation of IRs and their associated 95% CI for each cohort overall and stratified IRs by the variables listed in the main analyses (patient age, treatment duration, time since last exposure, and exposure to local hormone therapy). These stratified analyses will only be done once there are at least 4 events in both the *Duavee* and E+P HRT groups.

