New initiators of either *Duavee* or (E+P) HRT with evidence of unopposed estrogen therapy (i.e., estrogen HRT use without progestin use) in their baseline period, and no evidence of a hysterectomy, are not included in the main analyses. Patients with evidence of progestin use at anytime in their baseline period will not be categorized as having unopposed estrogen use. This group will be analyzed separately, because of the high likelihood of confounding by indication for the relationship of choice of study drug and the endometrial safety endpoints, and limitations of the data to identify hysterectomies that have occurred prior to a patient's baseline period. This results in an inability to accurately differentiate between patients with and without an intact uterus, both who have used unopposed estrogen. For a given safety endpoint, this analysis will only be done once there are at least four events in both the *Duavee* and E+P HRT groups.

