7.7.6. Statistical Methods

7.7.6.1. Descriptive Analysis

Baseline characteristics and reasons for censoring will be presented for each exposure group. Counts and percentages for categorical variables, and mean, median, standard deviation and range for continuous variables will be presented. Descriptive characteristics will be presented for the following groups:

1. All new users of *Duavee* and E+P HRT included in the cohort; and
2. All new users of *Duavee* and E+P HRT with prior E+P HRT exposure.

For those study reports that include data from the NDI where the period of time captured by NDI data is different from the study period available in the automated claims (See Figure), tables showing these characteristics during the interval when NDI data are available will also be included.

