7.7.6.2. Univariate/Unadjusted Analysis

As described in [Section 7.7.1](#) through [Section 7.7.2](#), IRs and their associated 95% CI overall and stratified by age, duration of treatment, time since most recent exposure and use of topical estrogen products will be presented.

For a given safety endpoint, HRs in either the univariate or multivariate analyses will not be performed until there is at least one event in both cohorts, and at least four events in total

(across cohorts). Until this threshold is reached, analyses will consist of cohort description and IR estimation.

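### The sub-analysis of women with baseline unopposed estrogen is withheld for an endpoint until both cohorts have four events, with no fallback, which conflicts with the protocol's other reporting rules and makes reporting depend on the outcome

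*Protocol*

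**What the plan says.** Section 7.7.2 of the protocol sets aside new initiators who used estrogen without progestin in the baseline period and have no evidence of hysterectomy. Its reasons are likely confounding by indication and the inability to see hysterectomies that predate the baseline period. For a given endpoint, "this analysis will only be done once there are at least four events in both the *Duavee* and E+P HRT groups". The condition covers the analysis as a whole, and nothing is said about what is given before it is met.

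Other sections treat the same matter differently:

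- **Prior E+P users (7.7.2).** Overall incidence rates (IRs) with intervals are planned without a threshold. The four-event condition applies to the breakdowns only: "These stratified analyses will only be done once there are at least 4 events in both the *Duavee* and E+P HRT groups".
- **General rule (7.7.6.2).** IRs described in 7.7.1 through 7.7.2 are to be presented overall and stratified. The threshold concerns hazard ratios (HRs): "HRs in either the univariate or multivariate analyses will not be performed until there is at least one event in both cohorts", with at least four in total. Below it, "Until this threshold is reached, analyses will consist of cohort description and IR estimation".
- **Design and eligibility (7.1, 7.2.1, 7.2.2).** Sub-analyses of women with baseline unopposed estrogen are promised without an event condition.
- **Descriptive groups (7.7.6.1).** Two are listed: the new users in the cohort, and "All new users of *Duavee* and E+P HRT with prior E+P HRT exposure". The unopposed-estrogen group is not named.

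**The concern.** These women are outside the primary comparison, so the sub-analysis is the only planned place for their results on the two primary endpoints. A rule that releases even a count and a crude rate only when both cohorts have reached four events has two consequences.

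First, whether anything is shown depends on the result. One to three Duavee events stay unreported whatever the ratio to the comparator. Second, a Duavee rate shown only because its count reached four is biased upward, and the bias is largest when the expected count is small.

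The stated reasons (confounding, uncertain uterine status) support separate analysis and restraint about an HR. They do not support holding back counts, person-time and crude rates. Prior E+P users also raise interpretive problems that 7.7.2 sets out at length, yet their overall rates are not gated.

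**Working it through.** **Reproducing Table 1 (7.5).** The protocol gives no projection for this group, so the check starts from Table 1. Take the tabulated endometrial cancer count D as the total, with p the Duavee share of users. The interval at a true HR of 1 is exp(±1.96 × √(1/(D·p·(1−p)))).

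| Report | Duavee / E+P users | D | p | Computed | Table 1 |
|---|---|---|---|---|---|
| 1 | 1,800 / 36,651 | 29 | 0.0468 | 0.18 to 5.60 | 0.18 to 5.60 |
| 2 | 3,600 / 44,122 | 62 | 0.0754 | 0.39 to 2.57 | 0.39 to 2.56 |
| 3 | 5,400 / 50,350 | 80 | 0.0969 | 0.48 to 2.10 | 0.48 to 2.10 |

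The intervals agree within 0.01. They imply D·p = 1.4, 4.7 and 7.7 endometrial cancers in the whole projected Duavee cohort, before any subgroup is taken.

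**Inputs for the gate.**
- Pilot rates, third report: 80/89,438 = 0.894 cancers and 399/89,438 = 4.461 hyperplasias per 1,000 person-years (PY).
- Duavee users at the final report: 7,200 (assumption; Table 1 adds 1,800 a year).
- Duavee PY, low: 7,200 × 10/12 = 6,000, using the 10 months in footnote a of Table 1.
- Duavee PY, longer: 7,200 × 89,438/50,350 = 7,200 × 1.776 = about 12,790. This is E+P-like follow-up, because 7.1 and 7.4 keep women at risk after discontinuation.
- E+P PY at the final report: about 120,000 (assumption, extrapolated from Table 1).
- Group size: not stated. Taken as 10%, 20% or 50% of the main cohort's size, the same fraction in both arms.
- Event rate in the group: not stated. Taken at the pilot rate, then at three times it.

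**Chance of at least four Duavee events,** P(X ≥ 4) with X Poisson:

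| Group size | 10% | 20% | 50% |
|---|---|---|---|
| Expected cancers, 6,000 PY | 0.54 | 1.07 | 2.68 |
| P(≥4) | 0.2% | 2.4% | 28% |
| P(≥4), triple rate | 8% | 40% | 96% |
| Expected cancers, 12,790 PY | 1.14 | 2.29 | 5.72 |
| P(≥4) | 3% | 20% | 82% |
| P(≥4), triple rate | 45% | 91% | over 99% |
| Hyperplasia P(≥4), 6,000 PY | 28% | 78% | over 99% |
| Hyperplasia P(≥4), 12,790 PY | 82% | over 99% | over 99% |

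**Which arm binds.** Expected E+P cancers at 10% size are 12,000 × 0.000894 = 10.7, so P(≤3) is 0.6%. At 20% size (21.5 expected) it is essentially zero. Except in a very small group (22% at 5% size), the Duavee count decides.

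**Break-even.** An even chance of four needs a Poisson mean of about 3.67, or 3.67/0.000894 = about 4,100 PY. That is 68% of 6,000 PY or 32% of 12,790 PY.

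**What is lost.** Take 10% size and 10 months per user: 600 Duavee PY against 12,000 E+P PY. Three Duavee against eight E+P cancers gives a rate ratio of (3/600)/(8/12,000) = 7.5. Given 11 events and a Duavee share of 600/12,600 = 0.048, the one-sided exact p is 0.013. The rule would leave this unanalysed. With the longer follow-up (1,279 PY) the same counts give a ratio of 3.5 and p of 0.08. In the low case, a true threefold excess (Duavee mean 1.61 or 3.22) is withheld with probability 92% at 10% size and 60% at 20%.

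**Upward bias.** At 20% size in the low case the mean is 1.07. Given at least four events, the expected count is 4.25, so a reported Duavee rate averages about four times the true one. At 50% size with longer follow-up the factor falls to 6.43/5.72 = 1.1.

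**The case against.** Four points on the other side carry weight.

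*Section 7.7.6.2 can be read as restoring the rates.* It refers to the IRs described through 7.7.2, which includes this group, and its fallback is not confined to the main cohort. A reader might infer that these women certainly get nothing; the documents do not settle that. But the generous reading contradicts 7.7.2, which is the specific rule, so the two still need reconciling. Likewise, absence from the descriptive groups is not certain. The first item in 7.7.6.1 could be read to include these women, 7.3.4 lists unopposed estrogen as a baseline variable, and Figure 4 and the table shells are not available here. The group is simply not named.

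*A reader might infer that endometrial cancer in this group will probably never be reported.* That cannot be derived, because neither the group's size nor its rate is given. The chances above run from 0.2% to over 99%, depending on size, follow-up and rate. The group could also have a lower endometrial rate, since 7.9 expects some women without a uterus in it.

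*A reader might infer that a large one-sided excess, such as seven Duavee against three E+P cases, would be hidden.* The rule permits it, but with so much more E+P person-time it is nearly unreachable. An excess with four or more Duavee events would normally be analysed. The exposure is confined to one to three Duavee events.

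*Caution about this group is justified.* The protocol expects strong confounding, and low rates over a denominator that includes women without a uterus could falsely reassure. This argues against an HR and for a caveat beside the rates. It does not argue for omitting counts and person-time.

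**Conclusion.** The concern holds as an internal conflict and an outcome-dependent reporting rule. Section 7.7.2 gates the whole unopposed-estrogen sub-analysis on four events in both cohorts. That is stricter than its own rule for prior E+P users and out of line with 7.7.6.2 and with the unconditional commitments in 7.1, 7.2.1 and 7.2.2. Applied literally, it suppresses results with one to three Duavee events and inflates the Duavee rates that pass.

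The size is conditional. For endometrial cancer at the pilot rate, with 7,200 Duavee users assumed, the gate is more likely missed than met while the group is smaller than about 32% (1.78 years per user) to 68% (10 months per user) of the Duavee cohort's size. A raised rate or a large group removes most of the problem, and hyperplasia is affected much less. The main comparison is untouched. It is a reporting defect in a sub-analysis, worth correcting because the correction is cheap and these women's primary-endpoint results have no other planned place.

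**What to change.** - In 7.7.2, state that every interim and final report gives for this group, by cohort and endpoint and whatever the event count: number of women, person-years, events, and overall IR with exact Poisson 95% CI. Place the caveat on uncertain uterine status beside these rates.
- Keep the four-events-in-both threshold for stratified IRs only, as for prior E+P users.
- Do not add an HR for this group under the looser main-analysis rule (one event per cohort, four in total). The protocol regards the group as highly confounded, and the neighbouring prior-E+P group gets IRs only.
- Align 7.7.6.2 with this wording, and name the group among the descriptive populations in 7.7.6.1.

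The cost is one more table per report from data already extracted. Intervals will be wide at low counts, which the exact CI makes visible, and small cells may need masking under data-use rules.

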7.7.3. Adjustment/Control of Confounding

As with any observational study, an important aspect of study design will be the methods used to ensure comparability of treatment groups and control for any confounding effects due to extraneous risk factors. To make full use of the extensive information in the HIRD pertaining to use of prescription medications, diagnoses, procedures, and inpatient as well as outpatient health care encounters, the analyses will use boosted regression to compute propensity scores.^{11,12} Boosted regression, a technique common in machine learning that has been more recently applied to propensity scores, provides for a more robust model that better balances treatment groups. Because it is a non-parametric approach, the impact of model assumptions on results and risks of model misspecification are minimized.

E+P HRT comparator subjects will be weighted according to their estimated probability of receiving *Duavee*, and adjusted analyses will use propensity score matching to balance the treatment groups on multiple factors simultaneously at the time of first dispensing of a study drug. The propensity score matched groups will be evaluated for balance and any patient restrictions done as a result of this matching will be described along with impact on generalizability. To avoid issues associated with model misspecification and improve comparability, the analyses will use doubly robust estimation procedures.¹¹

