7.7.1. Main Analyses

The analyses will describe patients that initiate *Duavee* and the comparator E+P HRT cohort with respect to demographic and clinical characteristics as enumerated in [Section 7.3.4](#). Reasons for censoring will also be described by exposure group. Descriptive comparisons of the two cohorts will be done to document their differences at baseline and to identify potential confounders to be addressed in the propensity matching.

For each of the primary endpoints (i.e., endometrial hyperplasia and endometrial cancer), an IR will be calculated as the number of women meeting a claims-based algorithm for each outcome (first event only) divided by person-time at risk.

The IR and its associated 95% CI will be presented for each cohort overall and stratified by categorical patient age at cohort entry, total duration of *Duavee* or E+P HRT treatment (long vs. short), time since last exposure to *Duavee* or E+P HRT, exposure to local hormone therapy (See Appendix 2), and by presence (Y/N) of an osteoporosis diagnosis within the 90 days before or after initiation of *Duavee* or E+P HRT. Duration of treatment and time since last exposure will be categorized based on observed data distributions. The feasibility of these stratifications and of a possible analysis that stratifies simultaneously by duration of treatment and time since last exposure will be determined based on the number of observed safety events.

Further details of the validation process are described in Appendix 3 and will be contained in the separate Endpoint Algorithm Development Report.

Hazard ratios will be estimated that represent the relative risk associated with initiating *Duavee* as compared to E+P HRT. It is planned to conduct both crude (unadjusted) and adjusted analyses to assess the HR for each of the primary endpoints. Adjusted analyses will use propensity score matching to ensure comparability between treatment groups. Further discussion of the methods to be used in computing propensity scores is included in [Section 7.7.3](#).

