7.7.6.3. Multivariate/Adjusted Analysis

Hazard ratios will be estimated, using Cox proportional hazards models, to explore the risk of first occurrence each safety endpoint in women newly exposed to *Duavee* when compared to initiators of E+P HRT, adjusted using propensity score matching.

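### Section 7.7.3 prescribes both weighting and matching without saying which gives the adjusted HR, and Table 1 gives precision only for the unmatched comparison

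*Protocol*

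**What the plan says.** Protocol section 7.7.3 sets out the confounding control. After boosted regression for the propensity score, one sentence states two methods: "E+P HRT comparator subjects will be weighted according to their estimated probability of receiving" Duavee, and then "adjusted analyses will use propensity score matching to balance the treatment groups on multiple factors simultaneously". The paragraph goes on to say that "any patient restrictions done as a result of this matching will be described along with impact on generalizability", and ends by adding that "the analyses will use doubly robust estimation procedures".

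The other two places that define the adjusted analysis mention only one of these methods. Section 7.7.1: "Adjusted analyses will use propensity score matching to ensure comparability between treatment groups". Section 7.7.6.3 describes the Cox model as "adjusted using propensity score matching".

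Section 7.5 projects precision in Table 1. Its comparator rows, including "Estimated person-years of follow-up for E+P HRT users", come from pilot analyses of all new E+P users in the database (footnote b). Neither matching nor weighting is mentioned. Section 7.5 and the Abstract then state that, for hyperplasia, the study could rule out an HR above 2.26, 1.56 and 1.39 at one, two and three years.

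**The concern.** Weighting and matching are different ways of using the propensity score. Weighting normally keeps all comparators and lets some count for less. Matching keeps a subset. The two can give different point estimates and standard errors, and possibly different target populations. As written, an analyst could follow section 7.7.3 with a weighted Cox model or a matched one, and nothing says how the two would be combined. The study issues cumulative annual reports, so the choice should not remain open once results are being seen.

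The second problem follows from the first. Section 7.9 warns of channelling between the products, so the adjusted HR is the one that addresses comparability. Yet the only precision figures in the protocol use the full comparator cohort. These figures carry weight: section 7.1 says the study duration was determined from them, and section 7.9 cites the size projection as a strength. A reader would take 1.39 as the limit expected for the adjusted hyperplasia HR at the third report, and the protocol gives no basis for that.

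**Working it through.** **Inputs (Table 1, Reports 1 / 2 / 3).** Duavee users 1,800 / 3,600 / 5,400. E+P users 36,651 / 44,122 / 50,350. E+P person-years 27,768 / 58,399 / 89,438. E+P hyperplasia events 129 / 274 / 399. E+P endometrial cancer events 29 / 62 / 80. Two-sided 95% intervals.

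**Formula.** Limits = HR × exp(±1.96 × SE), with SE = √(1/d_D + 1/d_E), where d_D and d_E are the Duavee and E+P event counts.

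**Step 1: reproduce the printed figures.** Footnote a gives 10 months per Duavee user, that is 1,500 / 3,000 / 4,500 person-years. At the E+P hyperplasia rate and HR = 1.0 this gives 6.97 / 14.08 / 20.08 Duavee events. With all E+P events the intervals are (0.47, 2.14), (0.59, 1.71) and (0.64, 1.57). The table prints (0.44, 2.26), (0.64, 1.56) and (0.72, 1.39), so it does not reproduce from its stated person-time. That is a separate matter. To isolate the effect of matching, I use the Duavee events that the printed limits themselves imply.

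**Step 2: implied Duavee events.** d_D = 1 / [(ln U / 1.96)² − 1/d_E], where U is the printed upper limit at HR = 1.0.

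- Report 1: 1 / (0.17306 − 0.00775) = 6.05
- Report 2: 1 / (0.05147 − 0.00365) = 20.91
- Report 3: 1 / (0.02823 − 0.00251) = 38.88
- Cancer, Report 3: 1 / (0.14329 − 0.01250) = 7.65

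**Step 3: is Table 1 a full-cohort projection?** The text indicates so, since footnote b takes users, person-time and events from the pilot cohort. The arithmetic agrees as far as it goes. If the Report 1 interval were a 1:1 matched one, it would need 2 / 0.17306 = 11.56 Duavee events. At 129/27,768 per person-year that is about 2,488 person-years, or 1.38 years per user within a 12-month first period, which is impossible. At 1:2 the figure is 1.04 years, also impossible. At 1:4 it is 0.86 years, which this check alone cannot exclude, so for higher ratios the conclusion rests on the text.

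**Step 4: matched precision.** The protocol gives no ratio, so 1:k with k = 1, 2, 4 is an assumption. At HR = 1.0, with matched women having the Duavee group's follow-up and event rate, d_E = k × d_D and SE = √[(1 + 1/k)/d_D].

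| Upper limit, HR = 1.0 | Printed | 1:4 | 1:2 | 1:1 |
|---|---|---|---|---|
| Hyperplasia, Report 1 | 2.26 | 2.44 | 2.65 | 3.09 |
| Hyperplasia, Report 2 | 1.56 | 1.61 | 1.69 | 1.83 |
| Hyperplasia, Report 3 | 1.39 | 1.42 | 1.47 | 1.56 |
| Cancer, Report 3 | 2.10 | 2.21 | 2.38 | 2.72 |

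Example, hyperplasia at Report 3, 1:1: SE = √(2/38.88) = 0.2268, and exp(1.96 × 0.2268) = 1.56. At 1:4: SE = √(1.25/38.88) = 0.1793, giving 1.42.

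**Step 5: how much depends on the ratio.** At Report 3 the variance of the log HR rises by a factor of 0.2268²/0.02823 = 1.82 at 1:1, but only 0.1793²/0.02823 = 1.14 at 1:4. With unlimited comparators the upper limit would still be exp(1.96/√38.88) = 1.37, so the Duavee events dominate.

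**The case against.** The strongest reply is that the matching ratio and caliper are ordinary detail for an analysis plan, that Duavee events drive the variance, and that at 1:4 the third-report limit moves only from 1.39 to 1.42. Section 7.5 itself warns that precision may change if uptake, event rates or follow-up differ. Section 7.7.1 plans crude as well as adjusted HRs, section 7.7.7 says that the aim is estimation, and Table 1 stops at the third report although a fourth year of data accrues.

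Much of that stands. The missing ratio is not a fault, and the loss may be modest. But the section 7.5 caveat does not cover the choice of estimator, and naming two methods differs from leaving one to be detailed later.

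Several stronger readings are tempting and not supported:

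- **Matching discards most E+P women.** This depends on the ratio. At Report 3, 1:4 keeps 21,600 of 50,350 (43%), while 1:5 keeps 27,000 (54%). Variable-ratio or full matching is not excluded.
- **The printed limits are far out of reach.** This is not so at 1:4. The 10-month inputs give 1.57 unmatched and 1.86 at 1:1, but the move from 1.39 to 1.57 occurs with every comparator kept and has nothing to do with matching.
- **Doubly robust estimation is a third rival estimator.** It adds an outcome model to a propensity-score method and can accompany weighting or matching.
- **Matching must go.** Three sections name it. Which method to keep is a trade-off that the documents do not settle.

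**Conclusion.** The concern holds in two parts. First, section 7.7.3 prescribes weighting and matching together without saying which yields the adjusted HR, and sections 7.7.1 and 7.7.6.3 mention matching only. This is plain from the text. Second, Table 1 and the rule-out statements in section 7.5 and the Abstract give the precision of the unmatched comparison, not of the adjusted HR that the plan specifies.

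The size is conditional. For assumed fixed ratios between 1:4 and 1:1 it runs from slight to material. At 1:1 the third-report hyperplasia limit (1.56) is no better than the one printed for the second report. These figures take Table 1's implied Duavee events at face value and assume that every Duavee user finds a match. Unmatched Duavee users would widen the intervals further. If weighting is the estimator instead, the loss depends on the spread of the weights, for which the documents give no figure.

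**What to change.** Name one primary adjusted estimator, in the same words, in sections 7.7.1, 7.7.3 and 7.7.6.3, and say how the doubly robust step attaches to it. Weighting all E+P women to the Duavee population is one option that keeps the comparator information, though extreme weights would need checking. Matching is another. The method not chosen becomes a sensitivity analysis or is removed.

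Then restate Table 1 and the rule-out sentences in section 7.5 and the Abstract for that estimator, giving the assumed matching ratio or effective comparator size. The minimum alternative is to label the current figures as applying to the unadjusted HR only.

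The cost is wording in three sections and a recalculated table, with no new data. The stated limits become somewhat less favourable.
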